4.5 REMOVAL, REPLACEMENT, OR EARLY DISCONTINUATION OF SUBJECTS FROM THERAPY OR ASSESSMENT

Subjects are free to discontinue their participation in the study at any time and without prejudice to further treatment. The Investigator must withdraw any subject from the study if that subject requests to be withdrawn, or if it is determined that continuing in the study would result in a significant safety risk to the subject. Withdrawn subjects will not be replaced.

The subject's participation in this study may be discontinued due to the following reasons:

- Subject withdraws consent.
- Intolerable adverse event (any subject experiencing a grade 3 or 4 infusion reaction will be withdrawn from the study).
- Subject's need for medication prohibited by the protocol.

- The Investigator decides that continuing in the study would not be in the subject's best interest.
- The subject is noncompliant with the protocol.
- The subject becomes pregnant.
- Upon the decision of relevant Regulatory Authorities and/or the Institutional Review Board/Independent Ethics Committee (IRB/IEC).

Subjects who progress and/or relapse will be withdrawn from the study at the Investigator's discretion and will be able to receive local standard-of-care.

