4.5.1 Handling of Early Discontinuation

If a subject is withdrawn from the study, either at his or her request or at the Investigator's discretion, or fails to return, every effort should be made to determine the reason. This information will be recorded on the subject's case report form (CRF). All subjects who withdraw from the study prematurely, regardless of cause, should undergo Early Discontinuation Study Visit (see Section 5.4). It is important to obtain follow-up data for any subject withdrawn due to an AE or abnormal laboratory test finding. In any case, every effort must be made to undertake safety follow-up procedures.

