5.1 SCREENING PERIOD (VISIT 1, DAY -28 TO DAY -1)

The purpose and procedures of the study will be fully explained to participating subjects. Those wishing to enroll in the study will sign a written informed consent prior to initiating any study related evaluations or procedures.

The following assessments will be done at the screening visit, up to 28 days before initiation of treatment (Day 0):

- Review and sign Informed Consent
- Assign screening number
- Inclusion and Exclusion Criteria
- Medical history and demographic data
- Prior and concomitant medications
- Physical examination (including vital signs, height and weight measurements)
- ECG
- Screen for active/latent tuberculosis (Interferon Gamma Release Assay)
- Screen for *C. Difficile* toxin in stool sample
- Flexible sigmoidoscopy with biopsies. At least 3 tissue samples are required from area of active inflammation. Additional biopsy samples may be obtained at the Investigator's discretion for histological assessment.
- Mayo score
- UCEIS
- Eotaxin-1 in tissue will be measured using two of the biopsy samples
- Eosinophil count in tissue will be measured histologically using the remaining biopsy sample
- Calprotectin in fecal sample
- Laboratory evaluations: hematology, biochemistry, serology and serum pregnancy test for females of childbearing potential.
- Eligible subjects will be randomized in a 2:1 ratio to one of two treatment arms, bertilimumab 10 mg/kg or matching placebo.

The screening visit may be conducted over multiple days. Screening visit data (Mayo score, UCEIS, eotaxin-1 and eosinophil count in tissue sample) will be considered baseline data for statistical analysis purposes.

5.2 TREATMENT PERIODⁱ: VISIT 2 (DAY 0), VISIT 3 (DAY 14) AND VISIT 4 (DAY 28)

At Visit 2 (Day 0), inclusion exclusion criteria will be reviewed.

The following assessments will be performed at each treatment visit (Day 0, Day 14 and Day 28) pre-dose:

- Physical examination
- Vital signs
- ECG
- Partial Mayo score
- Safety laboratory evaluations: hematology, biochemistry, antibodies to bertilimumab.
- Blood samples for eosinophil count^j, serum eotaxin-1, hs-CRP^k and ECP

Protocol: Immune/BRT/UC-01

Page 26 of 58 Final Version 8.0 May 23, 2018

ⁱ Visits 3 and 4 during the Treatment Period have a ± 2 day window.

^j Done using the hematology blood sample.

^k Done using the biochemistry blood sample.

- Blood samples for bertilimumab (PK analysis)
- Calprotectin in fecal samples

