5.4 EARLY DISCONTINUATION STUDY VISIT

An early discontinuation study visit will be performed for subjects who withdraw from the study for the reasons specified in Section 4.5.

All reasons for treatment discontinuation will be documented in the source documents as well as the CRF. Only one reason (the most severe) for early discontinuation should be recorded in the CRF. If one of the reasons for discontinuation is an AE – this should be chosen as the reason. Every effort should be made to follow-up these subjects for resolution of AE.

At this visit, flexible sigmoidoscopy with biopsies will be done in addition to the activities relating to the study period at which time the subject discontinuation visit will be performed. That is, if the subject discontinues during the Treatment period, the visit activities will be similar to those described in Section 5.2; likewise, if the subject discontinues during the Follow-up Period, the visit activities will be similar to those described in Section 5.3. Activities may include (but not limited to): AEs, concomitant medications, laboratory tests, vital signs, and physical examination. Appropriate procedures and evaluations will be completed as deemed necessary by the Investigator.

This visit may be performed on the same day as an originally scheduled visit or could be conducted separately. Data collection at these visits should primarily be guided according to principles to protect subject safety and well-being.

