7.2 SERIOUS ADVERSE EVENT

A **serious** adverse event (SAE) is any adverse event occurring at any dose that suggest a significant hazard or side effect, regardless of the Investigator or Sponsor's opinion on the relationship to the investigational product and that results in, but may not be limited to, any of the following outcomes:

- death (regardless of the cause)
- a life-threatening adverse drug experience
- inpatient hospitalization or prolongation of existing hospitalization (any inpatient hospital admission that includes a minimum of an overnight stay in a health care facility)
- a persistent or significant disability/incapacity

a congenital anomaly or birth defect.

Important medical events that may not result in death, be life-threatening or require hospitalization may be **serious** when, based upon appropriate medical judgment, they may jeopardize the subject and may require medical or surgical intervention to prevent one of the outcomes listed above.

Hospitalization for elective treatment of a pre-study condition that did not worsen while on study and hospitalizations for treatment of non-adverse events (e.g., cosmetic surgery) are not considered serious adverse events.

Significant medical events are those, which may not be immediately life-threatening, but may jeopardize the subject and may require intervention to prevent one of the other serious outcomes listed above. Examples of such events are intensive treatment in an emergency room or at home for allergic bronchospasm; blood dyscrasias or convulsions that do not result in hospitalization; resulting in an adverse event will normally be considered serious by this criterion.

Inpatient hospitalization or prolongation of existing hospitalization means that hospital inpatient admission and/or prolongation of hospital stay were required for treatment of AE, or that they occurred as a consequence of the event. Hospitalization for elective treatment of a pre-study condition that did not worsen while on study and hospitalizations for treatment of non-adverse events (e.g., cosmetic surgery or diagnostic procedure) are not considered serious adverse events.

Any new SAE that occurs after the study period and is considered to be related (possibly/probably) to the investigational product or study participation should be recorded and reported immediately.

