7.4 NOTIFICATION ABOUT SERIOUS OR UNEXPECTED ADVERSE EVENTS

All SAEs must be reported **immediately** to the Immune Pharmaceuticals representative as soon as it becomes known to the Investigator and not later than within 24 hours of their knowledge of the occurrence of an SAE. The notification will occur via data entry to the EDC with phone/fax/text/email notification to the Sponsor. Immune Pharmaceuticals Representative:

These preliminary reports will be followed within 24 hours by detailed descriptions that will include a completed SAE form, copies of hospital case reports, autopsy reports and other documents, when requested and applicable.

In addition, all AEs / SAEs / Suspected Unexpected Serious Adverse Reaction (SUSARs) will be reported to the local EC and regulatory authorities as required by local regulations and ICH-GCP guidelines.

Minimal information should include:

- An identifiable subject (e.g., Subject randomization number)
- An identifiable reporting source
- All related adverse events
- The suspect medicinal product
- Follow-up of SAEs / SUSARs
- Follow-up of SAEs / SUSARs that occur during the study will continue until their satisfactory resolution or stabilization.

If, when supplementary information is available, a follow-up SAE Report Form must be completed by the site and data entry inputted to the EDC with follow-up phone/fax/text/email to Sponsor within 24 hours.

The contact information for follow up SAE reporting is the same as for initial SAE reports (see above section).

The paper copy of the SAE form and accompanying documentation should be placed in the SAE section of the Investigator's file. If supplementary information on a SAE has to be sent, the SAE form has to be used marked as "follow-up report."

Follow-Up Reports on non-serious AEs

All AEs must be followed until resolution or stabilization. In outstanding cases, it may be defined as "ongoing without further follow-up" by the Investigator and Sponsor's decision.

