8.3.2 Subject Disposition

Major and minor protocol deviations will be identified by medically trained staff before the study closure. All screened subjects will be accounted for; enrolled subjects will be followed to completion. Protocol violations determining the belonging of subjects to the different analysis sets will be summarized. A full disposition tree will be generated displaying the number of subjects reaching the different phases of the study (screening, randomization/treatment, end of treatment, end of study) and the main reasons for exclusion.

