8.3.7 Safety Analysis

The evaluation of safety endpoints will be carried out on the Safety set. Safety will be assessed by evaluation of adverse events and changes from baseline in vital signs, physical examination, infusion reactionand clinical laboratory safety test results. Individual subject listing will be provided. The observation period for all the safety endpoints spans from start of study medication up to study day 90.

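### A grade 3 or 4 infusion reaction ends study participation, not only dosing, so no dated safety or antibody assessment to Day 90 is set after one undated Early Discontinuation visit

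*Protocol*

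**What the plan says.** Protocol Section 4.5 lists reasons for which participation may end. Within the item on intolerable adverse events it makes one case mandatory: "any subject experiencing a grade 3 or 4 infusion reaction will be withdrawn from the study". Appendix D separately tells the site to discontinue the infusion at grades 3 and 4.

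Withdrawn subjects should have an Early Discontinuation visit (Section 4.5.1). Its content is set in Section 5.4: "At this visit, flexible sigmoidoscopy with biopsies will be done in addition to the activities relating to the study period" in which the subject stopped. The schedule in Appendix A marks PK, antibodies, hematology and biochemistry, ECG and adverse events once at that visit and gives it no study day. SAP Table 1 repeats this.

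Beyond that visit:

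- Section 4.5.1 calls follow-up data after an adverse-event withdrawal important and adds: "In any case, every effort must be made to undertake safety follow-up procedures".
- Section 7.4: "All AEs must be followed until resolution or stabilization".
- Section 5.6.7 has clinically significant abnormal laboratory tests repeated as clinically indicated.
- Section 7.2 has the site report the following: "Any new SAE that occurs after the study period and is considered to be related (possibly/probably) to the investigational product" or to study participation.

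Section 8.3.7 sets the analysis window: "The observation period for all the safety endpoints spans from start of study medication up to study day 90". Section 8.3.2 says that "enrolled subjects will be followed to completion".

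**The concern.** Stopping further infusions after a severe reaction is plainly right, but a permanent stop of study drug achieves that. Ending study participation as well gives no further protection from dosing and gives up the planned safety observation of the subjects in whom late safety and antibody data are most informative.

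Safety is part of the primary objective (Section 2.1). Section 1.3.1 reports that no antibodies were detected in three earlier single-dose trials, whereas this trial gives three doses. A late seroconversion or a new late event in a subject with a severe reaction could go unseen. Section 8.3.7.1 divides treatment-emergent event counts by all subjects initially exposed, whatever their duration of exposure, so an unobserved event counts as no event. Section 8.3.7.3 reports antibody occurrence as a crude incidence rate and states no denominator.

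**Working it through.** **The plan's own figure.** The follow-up period is given as 62 days in the synopsis. Day 90 − Day 28 = 62 days, and 28 + 28 + 62 = 118 days, the stated study duration. Both reproduce.

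**Scheduled visits lost.** Inputs: post-Day-0 visits on Days 14, 28, 35, 42, 56 and 90 (Appendix A), and infusions on Days 0, 14 and 28. Visits lost = scheduled visits after the reaction day. Net loss = visits lost − 1 Early Discontinuation visit. Days = 90 − reaction day.

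| Reaction on | Dated visits lost | Number | Net | Days to Day 90 |
|---|---|---|---|---|
| Day 0 | 14, 28, 35, 42, 56, 90 | 6 | 5 | 90 |
| Day 14 | 28, 35, 42, 56, 90 | 5 | 4 | 76 |
| Day 28 | 35, 42, 56, 90 | 4 | 3 | 62 |

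**What the remaining provisions cover.** Sections 4.5.2, 5.4 and 7.4 follow events already known. Section 5.6.7 repeats laboratory tests already abnormal. Section 7.2 captures new events only if serious and judged related. Section 4.5.1 asks for effort but names no procedure, date or end point. Section 5.5 allows unscheduled visits during the study and sets none after withdrawal. None of these produces a dated antibody, PK, routine laboratory or ECG assessment, or routine collection of new non-serious events.

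**Drug exposure at the time sampling stops.** Section 1.3.1 gives a half-life of 16-20 days for total bertilimumab. From the reaction dose to Day 90:

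- Day 0: 90/20 to 90/16 = 4.5 to 5.6 half-lives.
- Day 14: 76/20 to 76/16 = 3.8 to 4.8.
- Day 28: 62/20 to 62/16 = 3.1 to 3.9.

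An Early Discontinuation visit on or near the reaction day would therefore be the last scheduled antibody sample while drug is still present. This assumes first-order decline and a full dose; a stopped infusion delivers less, and unbound drug has a shorter half-life (194-211 hours).

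**Weight of one subject.** At full enrollment of 42 randomized 2:1, the arms hold 28 and 14. One missed event is 1/28 = 3.6 percentage points on bertilimumab or 1/14 = 7.1 on placebo. This is the scale of one subject, not an estimate of bias.

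**The case against.** The strongest reply is that the protocol already covers these subjects. Section 4.5.1 addresses withdrawal for an adverse event directly, the observation window runs to Day 90, and Section 8.3.2 says enrolled subjects are followed to completion. A site reading these together could reasonably continue safety procedures to Day 90. The terms are also mixed: the title of Section 4.5 covers therapy or assessment, and Section 5.4 speaks of treatment discontinuation. The per-protocol set admits subjects with two of three doses and a Visit 7 Mayo score, so staying on after a missed dose is contemplated. Withdrawal after a severe reaction is a cautious phase 2a rule, and the safety analysis is descriptive.

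Much of this stands as a reason to rate the point low. It does not close the gap. The grade 3-4 rule is explicit, Section 8.3.2 is a disposition statement that sets no visit for withdrawn subjects, and the SAP adds no follow-up for them.

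Stronger readings are tempting but unsupported:

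- **No safety follow-up at all.** The provisions above contradict this. Only dated and routine assessment is missing.
- **A biased infusion-reaction rate, or no antibody data around the reaction.** The reaction itself is recorded. Section 5.2 requires pre-dose samples on each dosing day ("Safety laboratory evaluations: hematology, biochemistry, antibodies to bertilimumab"), and the Early Discontinuation visit adds another.
- **A computable number of affected subjects.** Section 1.3.2 reports three infusion reactions, one serious, without a denominator or a grade. It does not tie them to the 45 IV-exposed subjects of Section 1.2.2, and the benign safety statements in Sections 1.2.2 and 1.3.1 fit poorly with that denominator.
- **A specific efficacy loss through the SAP's four-week imputation window.** The Early Discontinuation visit has no fixed date, the window is measured from a Visit 7 date that a withdrawn subject may not have, and the question applies to every early discontinuer.

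**Conclusion.** The point holds as a minor one. A stated rule, not missing detail, ends scheduled safety observation after a grade 3 or 4 infusion reaction, with a net loss of 5, 4 or 3 dated assessments for a reaction on Day 0, 14 or 28. The consequence is confined to capture of late safety events and antibodies in these subjects. The number affected cannot be derived from the documents. It is probably small, and since the protocol defines study drug as either bertilimumab or placebo, both arms are covered. The visit counts rest on the nominal schedule and on exactly one Early Discontinuation visit being done; best-effort follow-up at some sites would reduce the loss.

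**What to change.** In Protocol Sections 4.5 and 5.4, replace study withdrawal after a grade 3 or 4 infusion reaction with permanent discontinuation of study drug. With the subject's consent, keep the remaining scheduled visits to Day 90, without infusion, for adverse-event, laboratory, ECG, antibody and PK assessment. The Day 56 sigmoidoscopy can be optional and waived if one was done at an Early Discontinuation assessment. A subject who also chooses to leave the study still has the full Early Discontinuation visit. If the withdrawal rule is kept, add at minimum one dated safety and antibody visit at Day 90, which would show late seroconversion still detectable then and prompt for new events.

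The cost is amendment wording and 4 to 6 already planned visits per affected subject. There are two downsides: later events are harder to attribute to study drug, and data collected after new ulcerative colitis treatment must be flagged.

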4.5.1 Handling of Early Discontinuation

If a subject is withdrawn from the study, either at his or her request or at the Investigator's discretion, or fails to return, every effort should be made to determine the reason. This information will be recorded on the subject's case report form (CRF). All subjects who withdraw from the study prematurely, regardless of cause, should undergo Early Discontinuation Study Visit (see Section 5.4). It is important to obtain follow-up data for any subject withdrawn due to an AE or abnormal laboratory test finding. In any case, every effort must be made to undertake safety follow-up procedures.

4.5.2 Adverse Events

Any serious AE (SAE) must be reported to the Sponsor or Sponsor's designee (by telephone/fax/text/email) as well as by inputting to the EDC within 24 hours; the IRB/IEC must be notified as required, according to site's regulations (for SAE notification procedures, refer to 7.4).

In the event of any AEs considered to be clinically significant by the Investigator, subjects will be followed up with appropriate medical management until the outcome is determined or stabilized, according to the Investigator's clinical judgment. All follow-up information will be recorded in the subject's CRF until resolution of the AE. Subsequent follow-up will be documented in the subject's personal file.

4.6 SPONSOR'S TERMINATION OF STUDY

The Sponsor reserves the right to discontinue the study at any time at the participating centers for any reason. Regulatory Authorities also have the right to terminate the study for any reason.

5. STUDY PROCEDURES AND ASSESSMENTS

The schedule of events for this study is shown in Appendix A. No protocol related procedures, including cessation of prohibited concomitant medications should be performed before subjects provide written informed consent. Study related events and activities including specific instructions, procedures, concomitant medications, dispensing of study medication and descriptions of AEs should be recorded in the appropriate source documents and CRF. The total amount of blood drawn during this study and by study visit is detailed in the Laboratory Manual.

5.1 SCREENING PERIOD (VISIT 1, DAY -28 TO DAY -1)

The purpose and procedures of the study will be fully explained to participating subjects. Those wishing to enroll in the study will sign a written informed consent prior to initiating any study related evaluations or procedures.

The following assessments will be done at the screening visit, up to 28 days before initiation of treatment (Day 0):

- Review and sign Informed Consent
- Assign screening number
- Inclusion and Exclusion Criteria
- Medical history and demographic data
- Prior and concomitant medications
- Physical examination (including vital signs, height and weight measurements)
- ECG
- Screen for active/latent tuberculosis (Interferon Gamma Release Assay)
- Screen for *C. Difficile* toxin in stool sample
- Flexible sigmoidoscopy with biopsies. At least 3 tissue samples are required from area of active inflammation. Additional biopsy samples may be obtained at the Investigator's discretion for histological assessment.
- Mayo score
- UCEIS
- Eotaxin-1 in tissue will be measured using two of the biopsy samples
- Eosinophil count in tissue will be measured histologically using the remaining biopsy sample
- Calprotectin in fecal sample
- Laboratory evaluations: hematology, biochemistry, serology and serum pregnancy test for females of childbearing potential.
- Eligible subjects will be randomized in a 2:1 ratio to one of two treatment arms, bertilimumab 10 mg/kg or matching placebo.

The screening visit may be conducted over multiple days. Screening visit data (Mayo score, UCEIS, eotaxin-1 and eosinophil count in tissue sample) will be considered baseline data for statistical analysis purposes.

5.2 TREATMENT PERIODⁱ: VISIT 2 (DAY 0), VISIT 3 (DAY 14) AND VISIT 4 (DAY 28)

At Visit 2 (Day 0), inclusion exclusion criteria will be reviewed.

The following assessments will be performed at each treatment visit (Day 0, Day 14 and Day 28) pre-dose:

- Physical examination
- Vital signs
- ECG
- Partial Mayo score
- Safety laboratory evaluations: hematology, biochemistry, antibodies to bertilimumab.
- Blood samples for eosinophil count^j, serum eotaxin-1, hs-CRP^k and ECP

Protocol: Immune/BRT/UC-01

Page 26 of 58 Final Version 8.0 May 23, 2018

ⁱ Visits 3 and 4 during the Treatment Period have a ± 2 day window.

^j Done using the hematology blood sample.

^k Done using the biochemistry blood sample.

- Blood samples for bertilimumab (PK analysis)
- Calprotectin in fecal samples
- Urine pregnancy test (for females of childbearing potential)

Subjects will receive a pretreatment regimen for infusion reaction prophylaxis. The regimen is as follows:

- Dexamethasone 10 mg PO 24-18 hours prior to administration of study drug.
- Acetaminophen 1000 mg PO 1 hour prior to administration of study drug.
- Either loratedine 10 mg PO or cetirizine 10 mg PO one hour prior to the administration of study drug.

In the event that dexamethasone was not administered previously, then 10 mg dexamethasone IV may be administered 1-3 hours prior to study drug administration.

Following completion of pre-dose assessments and administration of pretreatment regimen according to the appropriate timelines above, study drug will be administered by IV infusion over 30 minutes.

Subjects will remain in the clinic for up to 4 hours following completion of the 30 minutes IV infusion for PK assessment and safety follow-up. The following procedures will be conducted post-dose:

- Vital signs: 15 minutes (during infusion), 30 (+ 15) minutes (immediately post-infusion), 2 hr (±20 minutes) and 4 hr (±20 minutes) following initiation of study drug infusion.
- ECG at 30 (+15) minutes after initiation of study drug infusion.
- Blood samples for bertilimumab (PK analysis) at 30 (+15) minutes (immediately post-infusion) and 4 hours (±20 minutes) following initiation of study drug infusion.
- Recording of AEs (including post-infusion reactions, if applicable) and concomitant medications.

5.3 FOLLOW-UP PERIOD¹: VISIT 5 (DAY 35), VISIT 6 (DAY 42), VISIT 7 (DAY 56) AND VISIT 8 (DAY 90)

Subjects will be followed for 3 months post first study drug administration. The following assessments will be performed at the follow-up visits:

- Physical exam
- Vital signs
- ECG
- AE and concomitant medication recording
- Partial Mayo score (at Visits 5, 6 and 8)
- Safety laboratory evaluations: hematology, biochemistry, antibodies to bertilimumab
- Blood samples for eosinophil count, serum eotaxin-1ⁱ, hs-CRP^j and ECP
- Blood samples for bertilimumab (PK analysis)
- Calprotectin in fecal samples
- Flexible sigmoidoscopy with biopsies. On Day 56 (or early discontinuation visit), at least 3 tissue samples are required from the same region where the Screening

¹ Visits during the Follow-Up Period have a ±3 day window.

biopsies were obtained. Additional biopsy samples may be obtained at the Investigator's discretion for histological assessment.

- Eotaxin-1 in tissue will be measured using 2 of the biopsy samples (Visit 7 only)
- Eosinophil count in tissue will be measured histologically using the remaining biopsy sample (Visit 7 only).
- Mayo score (Visit 7 only)
- UCEIS (Visit 7 only)

